#### Description of Xofluza treatment schedule:

Xofluza will be administered as a single oral dose as soon as possible and within 48-hours of influenza symptom onset. Dosing will be delivered based on the package insert.:

Patient Body Weight (kg)	Recommended Single Oral Dose in Patients 5 years of Age and Older (Tablets)
20 kg to less than 80 kg	One 40 mg tablet (blister card contains one 40 mg tablet)
At least 80 kg	One 80 mg tablet (blister card contains one 80 mg tablet)

### **3.2 END OF STUDY AND LENGTH OF STUDY**

The end of this study is defined as the date when 12 weeks of mobile testing and treating deployment has concluded or the end of “influenza season” as defined by the New Mexico Department of Health, whichever is last. As this is a single dose observational study, there are no follow-up visits scheduled as part of the study. All subjects receiving the therapeutic will receive a follow-up phone call 24-48 hours following administration of Xofluza. All enrolled subjects will receive a follow-up phone call 14-days following the initial screening visit to assess symptom resolution and socioeconomic impact of their test result. The end of the study is expected to occur 12 months after the last patient is enrolled to allow for complete data analysis and evaluation. In addition, the Investigator may decide to terminate the study at any time.

The total length of the study, from screening of the first patient to the end of the study, is expected to be approximately 15 months.

### **3.3 RATIONALE FOR STUDY DESIGN**

#### **3.3.1 Rationale for Xofluza Dose**

The dose of Xofluza for this study was selected based on the Xofluza package insert.

#### **3.3.2 Rationale for Patient Population**

As described above, treatment with Xofluza has been shown to reduce viral load and symptoms in patients with influenza A or B. Therefore, this study was designed to see if a test and treat model would have significant impact on community transmission in socially vulnerable communities.

The inclusion criteria limit index patients to those with symptom onset within 48 hours. This is because it is believed that Xofluza will be most effective at preventing viral transmission if given early in the course of infection. (This 48-hour period is also consistent with the labels approved to date for Xofluza in countries including the US, Hong Kong, and Japan).

The study eligibility criteria allow for the inclusion of index patients who are minors. This is also consistent with the labels approved to date for baloxavir marboxil, which is approved for use in individuals aged  $\geq 5$  years of age.

## **4. MATERIALS AND METHODS**

### **4.1 PATIENTS**

Approximately 600-1,200 patients will be enrolled in the study to be screened for influenza A&B and SARS-CoV2. We expect approximately 10% positivity rate for 60-120 patients to be eligible for treatment.

There are approximately 140 census tracts in the Albuquerque Metropolitan Area that will be tracked during this study.

Zip Code	Race/Ethnicity (% population)							
	Hispanic	Non-Hispanic/White	Black	Native Indian	Asian	Hawaiian	Other	2 or More
87108	51.5	33.7	3.7	4.7	1.4	0.0	0.2	2.6
87123	44.3	40.7	3.5	3.5	4.6	0	0.1	3.7
87121	82.5	9.7	2.3	3.8	0.4	0.2	0.1	1
87102	61.4	26.6	3.1	5.6	10.7	0	0.31	1.5
87105	79.6	14.1	0.6	4.4	0.3	0.1	0.1	0.6
87106	38.1	48.2	3.3	3.1	3.9	0	0.5	2.9

#### **4.1.1 Inclusion Criteria**

Patients must meet the following criteria for study entry:

- Adult patients: Signed informed consent by any patient capable of giving consent, or, where the patient is not capable of giving consent, by his or her legal/authorized representative.
- Adolescent patients not able to legally consent: written informed consent for study participation is obtained from patient's parents or legal guardian, with assent as appropriate by the patient, depending on the patient's level of understanding and capability to provide assent
- Age  $\geq$  5 years at the time of signing the Informed Consent Form/Accent Form
- Ability to comply with the study protocol, in the investigator's judgment.
- Presence of (a) fever ( $\geq$ 38.0 °C per tympanic or rectal thermometer;  $\geq$ 37.5 °C per axillary, oral or forehead/temporal thermometer) or (b) any influenza symptoms (cough, sore throat, nasal congestion, headache, feverishness or chills, muscle or joint pain, fatigue).
- The time interval between the onset of fever or influenza symptoms and the pre-dose examinations is 48 hours or less.
- For women of childbearing potential: Agreement to remain abstinent (refrain from heterosexual intercourse):

Women must remain abstinent or use contraceptive methods with a failure rate of < 1% per year during the treatment period and for 28 days after the last dose of study treatment. Hormonal contraceptive methods must be supplemented by a barrier method.

A woman is considered to be of childbearing potential if she is postmenarcheal, has not reached a postmenopausal state ( $\geq 12$  continuous months of amenorrhea with no identified cause other than menopause), and has not undergone surgical sterilization (removal of ovaries and/or uterus).

Examples of contraceptive methods with a failure rate of  $< 1\%$  per year include bilateral tubal ligation, male sterilization, hormonal contraceptives that inhibit ovulation, hormone-releasing intrauterine devices, and copper intrauterine devices.

The reliability of sexual abstinence should be evaluated in relation to the duration of the clinical trial and the preferred and usual lifestyle of the patient. Periodic abstinence (e.g., calendar, ovulation, symptothermal, or postovulation methods) and withdrawal are not acceptable methods of contraception.

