Using a longitudinal patient database with an active system to prospectively geocode addresses entered into our system, we are able to determine, at the census tract level, neighborhoods that are at high risk for viral transmission because they are a hot spot or testing desert. We are then able to incorporate the social vulnerability index as an additional weighted measure to the hot spot or desert score in order to calculate an identified hot spot or desert risk for a census tract. Through collaboration with local community centers, we are able to deploy a mobile testing unit to a community center, park or senior center that is in close proximity to the identified neighborhood for rapid onsite testing for Influenza A&B and SARS-CoV2 using the cobas Liat system.

New Mexico has adopted “New Mexico Board of Pharmacy Protocol for Pharmacists Prescribing of Dangerous Drugs in Conjunction with Point of Care Testing” (NMBOP POCT Protocol, Appendix 5) that allows pharmacists the prescriptive authority to prescribe Influenza antiviral therapy in conjunction with a positive point of care test (POCT). TriCore employs two (2) on-site clinical pharmacists who will follow all of the pharmacist mandates included in the regulation to prescribe and distribute Xofluza according to the approved protocol in the test-to-treat model presented in this study. The NMBOP PCOT Protocol documents the eligibility and requirements of the certified prescribing pharmacists (pharmacist) following this protocol.

The pharmacist will perform a screening physical assessment, health assessment and medical history for the patient. If the subject meets the inclusion criteria, they will have a point of care test performed. If the subject meets the exclusion criteria, they will be excluded from the study. Testing will be performed using the cobas® SARS-CoV-2 & Influenza A/B assay on the cobas® Liat® system from a self-collected nasal swab. Subjects who test positive for influenza A or B will be prescribed Xofluza with no additional refills. The pharmacist will follow-up with the patient 24-48 hours following administration for evaluation of

signs/symptoms and will refer the patient to their primary care provider, provider, or clinic for recommended laboratory testing and follow-up if appropriate.

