All subjects eligible for Xofluza will receive patient education and counseling on drug information, adherence, side effects, and other patient educational materials, as appropriate. All subjects eligible for influenza antiviral therapy, but having contraindications to the therapy, or do not wish to use the therapy will be referred to their primary care provider, provider, or clinic for further evaluation.

Subjects testing positive for SARS-CoV-2 will be preferred by the pharmacist to the subjects' primary care provider, provider, or clinic for further medical assessment and follow-up, if appropriate. Subjects testing negative for all targets (SARS-CoV-2 and Influenza A&B) with a high index of suspicion for influenza, will be referred by the pharmacist to the subjects' primary care provider, provider, or clinic for further medical assessment and follow-up, if appropriate. All subjects will receive a follow-up call 14-days following the study visit to assess their symptom resolution and the impact of their illness on their well-being (Appendix 1).

The mobile testing unit will be deployed a minimum of 2 times per week following the determination of the influenza season by the New Mexico Department of Health. We expect to screen 50-100 patients per week for the duration of the influenza season (approximately 12 weeks) for a total of 600-1,2000 patients. With an anticipated 10% positivity rate for influenza, we expect at least 5-10 patients per week to be eligible for treatment for a total of 60-120 subjects eligible over the course of the study. All subjects will be provided a survey to evaluated their ability to access respiratory virus testing and their acceptance of and trust in using a mobile unit for access to treatment and therapeutics. Patients positive for SARS-CoV-2 will be counseled on options for treatment and follow up for COVID-19 infection. All subjects enrolled in the study will receive a follow-up phone call 14-days following the initial screening visit.

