#### **4.1.2 Exclusion Criteria**

Patients who meet any of the following criteria will be excluded from study entry:

- Patients who have received more than 48 hours of antiviral treatment for the current influenza infection prior to screening
- Patients who have received Xofluza for the current influenza infection
- Known contraindication to neuraminidase inhibitors
- Patients weighing  $< 20$  kg
- Patients unable to swallow tablets
- Patients with known severe renal impairment (estimated glomerular filtration rate  $< 30$  mL/min/1.73 m $^2$ ) or receiving continuous renal replacement therapy, hemodialysis, peritoneal dialysis
- Patients with any of the following laboratory abnormalities detected within 24 hours prior to or during screening (according to local laboratory reference ranges:
  - ALT or AST level  $> 5$  times the upper limit of normal (ULN)  
OR
  - ALT or AST  $> 3$  times the ULN and total bilirubin level  $> 2$  times the ULN
- Pregnant or breastfeeding, or positive pregnancy test in a predose examination, or intending to become pregnant during the study or within 28 days after the last dose of study treatment
- Exposure to an investigational drug within 5 half-lives or 30 days (whichever is longer) of randomization
- Any serious medical condition or abnormality in clinical laboratory tests that, in the investigator's judgment, precludes the patient's safe participation in and completion of the study
- Known hypersensitivity to Xofluza (baloxavir marboxil) or the drug product excipients

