## **6. STATISTICAL CONSIDERATIONS**

### **6.1 DETERMINATION OF SAMPLE SIZE**

The algorithms that we use to determine the community of interest is based on meeting the hot-spot or testing desert criteria and a weighted value of the social vulnerability index (SVI) which defined from 0-1.0 and is determined at the census tract level. This includes factors such as socioeconomic status, household composition, race/ethnicity, housing and transportation access. Each census tract is composed of 2500-4000 individuals and we anticipate enrolling 200-250 patients at each deployment resulting in approximately 5-10% of the census tract tested at each deployment. The 20 community centers that we will partner with have an average SVI pf 0.85 (0.55-1.0). There are

approximately 140 census tracts in the Albuquerque Metropolitan Area that will be tracked during this study. These high vulnerability locations are aggregated in six zip codes with the following demographic composition of race and ethnicity.

While test positivity rate will change based on the current epidemiology, we expect 10-20% positivity for Influenza during the treatment study period as we anticipate beginning the study period during respiratory virus season with increased viral positivity. Based on this, we expect 20-50 patients will be eligible for influenza treatment at each deployment with an additional 20-50 patients positive for COVID-19 who will receive referrals for COVID-19 treatment at other treatment locations. We expect that we will be able to provide treatment to approximately 430 individuals based on the assumption that 90% will be in the treatment window and 80% will test positive.

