The mobile testing unit will be deployed a minimum of 2 times per week following the determination of the influenza season by the New Mexico Department of Health. We expect to screen 50-100 patients per week for the duration of the influenza season (approximately 12 weeks) for a total of 600-1,2000 patients. With an anticipated 20-10% positivity rate for influenza, we expect at least 5-10 patients per week to be eligible for treatment for a total of 60-120 patients eligible over the course of the study. All subjects will be provided a survey to evaluated their ability to access respiratory virus testing and their acceptance of and trust in using a mobile unit for access to treatment and therapeutics. As per the New Mexico Test to Treat protocol, all patients will receive a follow-up phone call 24-48 hours following treatment. Additionally, all patients enrolled in the study will receive a follow-up phone call 14-days following the initial screening visit.

	Enrollment per deployment	Number of Deployments	Total Enrolled	Positivity Rate (Influenza)	Within Treatment Window	Expected Treated (total study)
Influenza Test to Treat	50-100	12	600-1200	10-20% (60-240)	90%	54-180

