**MUST HAVE CONSENT AND PATIENT MUST MEET CRITERIA TO CONTINUE**

Physical assessment and medical history documented

\_\_\_ YES \_\_\_ No

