#### VISIT COMPLETION

Survey returned: \_\_\_ YES \_\_\_ No

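### Onset within 48 hours is a condition of entry and so of testing, yet the Section 6.1 table allows for tested positives past 48 hours, and its 54–180 treated fits neither rule

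*Combined protocol and SAP*

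**What the plan says.** Section 4.1.1 (Inclusion Criteria) places this item among the conditions for study entry: "The time interval between the onset of fever or influenza symptoms and the pre-dose examinations is 48 hours or less". Section 3.3.2 confirms that the limit is an inclusion criterion. It justifies it by the benefit of giving the drug early and by consistency with approved labels.

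Section 3.1 sets the order of events: "If the subject meets the inclusion criteria, they will have a point of care test performed". It then has influenza positives prescribed Xofluza, with no check of the window between the result and the prescription. The case report form in Appendix 1 repeats the stop, "MUST HAVE CONSENT AND PATIENT MUST MEET CRITERIA TO CONTINUE", above the testing block. The item "Survey returned" comes below that block, at visit completion.

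Section 6.1 works differently. Its text assumes that "90% will be in the treatment window". Its table runs from total enrolled (600–1,200) to influenza positivity (10–20%, printed as 60–240), then to a column headed "Within Treatment Window" (90%), and ends at 54–180 expected treated.

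**The concern.** If nobody past 48 hours can enter, every enrolled positive is in the window at examination, and a 90% factor applied to enrolled positives has nothing to act on. If the factor is right, late people are being enrolled and tested against the entry criteria. Staff following Section 4.1.1 and staff following the table would test different people.

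Section 3.1 shows a similar blur. Subjects "having contraindications to the therapy, or do not wish to use the therapy will be referred" to a provider, yet Section 4.1.2 already removes several such people at entry, for example "Patients unable to swallow tablets". The plan nowhere separates who is tested from who is treated.

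Two things are at stake. The first is the treated forecast, which drives drug supply and the size of the safety population. The second is the scope of the access conclusions. Section 2.1 names better access to influenza diagnostics, and Section 2.2 makes experience of access to testing and therapeutics the secondary objective. If late attenders are outside the study, those conclusions describe only people who came promptly, and the plan does not say so. The stated reason for 48 hours concerns drug effect and labelling. It supports limiting treatment; no section gives a reason for limiting testing.

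**Working it through.** **Inputs (Section 6.1 table unless stated)**
- Enrolled: 600–1,200. Section 4.1 also describes these people as enrolled in order to be tested.
- Influenza positivity: 10–20%.
- Share in the treatment window: 90%, in both table and text, with no source given.
- Printed expected treated: 54–180.

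**1. Reproduce the printed forecast.** Treated = enrolled × positivity × share in window.
- Lower end: 600 × 0.10 × 0.90 = 54, which matches.
- Upper end: 1,200 × 0.20 × 0.90 = 216, not 180.
- To reach 180 at 90% in the window needs 180 / 0.90 = 200 positives, or 200 / 1,200 = 16.7% positivity. From the table's own 240 positives it needs 180 / 240 = 75% in the window. Neither figure appears in the plan.

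**2. Late positives implied by the table.** Enrolled × positivity × (1 − 0.90).
- 600 × 0.10 × 0.10 = 6.
- 1,200 × 0.20 × 0.10 = 24.

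The entry rule sets this group at zero.

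**3. Forecast under each rule.**

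| Rule | Share in window among enrolled positives | Expected treated |
|---|---|---|
| 48 hours governs entry | 100% | 600 × 0.10 = 60 to 1,200 × 0.20 = 240, before refusals |
| 48 hours governs dosing only | 90% | 54 to 216, with 6–24 late positives referred |
| Printed | 90% | 54–180 |

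Sections 3.1 and 4.1 expect 60–120 people eligible for treatment at 10% positivity. That is 600 × 0.10 and 1,200 × 0.10 with no reduction for the window, so those sections count as if the entry rule applied.

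**4. How many people the entry rule turns away.** The only late share that can be drawn from the plan is 10%, the complement of 90%. Applying it to all symptomatic attenders is an assumption.
- If 600–1,200 is the number enrolled: 600 / 0.9 = 667 and 1,200 / 0.9 = 1,333 must attend, so 67–133 are turned away.
- If 600–1,200 is the number attending: 600 × 0.10 = 60 to 1,200 × 0.10 = 120 are turned away.

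Together the range is 60–133. The 90% has no stated source, so the true number could be well outside it. At an assumed 70% in the window, 180–360 of 600–1,200 attenders would be turned away.

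**The case against.** **Testing only treatable people is a legitimate design.** This is a test-to-treat model, and Section 1.3 treats prompt access to therapy inside the 48-hour window as necessary. That stands: the entry rule is defensible. What is not defensible is a table that assumes a different rule.

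**The text may be ambiguous rather than a clear bar.** Section 4.5.5 ties RT-PCR to eligibility, which could suggest testing before eligibility is settled, and the criterion is timed to pre-dose examinations. But Section 4.5.5 conflicts with the order in Section 3.1 and does not take 48 hours off the entry list. Slippage between examination and dosing is an unlikely source of the 10%, since testing is rapid and on site.

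**Multiplication has no order.** If 600–1,200 were people approached, 600 × 0.90 × 0.10 = 54 would agree with an entry rule, and Sections 3.1 and 6.1 do speak loosely of screening that number. However, the table heads the column as enrolled, and Section 4.1 says the same. On this reading only 540–1,080 would be tested, and the upper end would still be 216.

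**What a reader might infer.** One might conclude that late attenders are definitely not surveyed, and that the survey therefore understates access barriers by some number of points. The documents do not support that. No sentence denies screening failures a survey; Sections 2.2, 3.1 and 6.1 promise one to all patients or subjects, and the form item records return, not offer. The exclusion is inferred from form order. The plan gives no barrier rate for late or prompt attenders. Late arrival may reflect access trouble or merely mild illness, so the bias could be zero.

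One might also count missed influenza cases among those turned away. That would require assuming the table's positivity in late attenders, and nothing bars testing elsewhere.

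**Conclusion.** The inconsistency holds. Sections 4.1.1, 3.3.2 and 3.1 and the case report form make 48 hours a condition of entry and hence of testing; the Section 6.1 table allows for 6–24 tested positives whom that rule excludes. The printed 54–180 matches neither rule: it should read 60–240 before refusals, or 54–216. These figures use only the table's inputs.

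The 60–133 people turned away rests on carrying the plan's unsourced 10% late share over to all attenders. The effect on the survey is a matter of scope, of unknown size. Nothing here shows an effect on the dose given, the definition of the safety population or the census-tract hot spot score. Nor does it follow that the entry rule is the wrong choice. The point is worth acting on because the correction is cheap and a reader cannot now tell whom the study tests.

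**What to change.** Choose one rule and make Sections 3.1, 4.1.1 and 6.1 and the case report form agree.

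**(a) Keep 48 hours as an entry criterion.**
- Delete the 90% column and restate expected treated as 60–240 before refusals.
- Report from the screening log (Section 4.5.1) how many people were turned away as late.
- State that the survey and access conclusions apply only to people who reached the unit within 48 hours.

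The cost is text and one count from a log already planned.

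**(b) Make 48 hours a treatment criterion, if the table reflects the intent.**
- Move the limit out of study entry and check it after the test, in Section 3.1 and on the form.
- Refer late positives.
- Restate expected treated as 54–216.
- Show survey results for onset of 48 hours or less versus more.

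The cost is test capacity, surveys and 14-day calls for people who cannot be treated on site: about 60–133 if 10% of all attenders are late. No extra drug is needed. Before adopting (b), the sponsor must confirm that it fits the pharmacy board protocol in Appendix 5, which is not available for this review. The sponsor should also check whether mobile-unit tests feed the hot spot score, since extra tests only in intervention tracts could raise detected cases there relative to matched tracts.

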#### **4.1.2 Exclusion Criteria**

Patients who meet any of the following criteria will be excluded from study entry:

- Patients who have received more than 48 hours of antiviral treatment for the current influenza infection prior to screening
- Patients who have received Xofluza for the current influenza infection
- Known contraindication to neuraminidase inhibitors
- Patients weighing  $< 20$  kg
- Patients unable to swallow tablets
- Patients with known severe renal impairment (estimated glomerular filtration rate  $< 30$  mL/min/1.73 m $^2$ ) or receiving continuous renal replacement therapy, hemodialysis, peritoneal dialysis
- Patients with any of the following laboratory abnormalities detected within 24 hours prior to or during screening (according to local laboratory reference ranges:
  - ALT or AST level  $> 5$  times the upper limit of normal (ULN)  
OR
  - ALT or AST  $> 3$  times the ULN and total bilirubin level  $> 2$  times the ULN
- Pregnant or breastfeeding, or positive pregnancy test in a predose examination, or intending to become pregnant during the study or within 28 days after the last dose of study treatment
- Exposure to an investigational drug within 5 half-lives or 30 days (whichever is longer) of randomization
- Any serious medical condition or abnormality in clinical laboratory tests that, in the investigator's judgment, precludes the patient's safe participation in and completion of the study
- Known hypersensitivity to Xofluza (baloxavir marboxil) or the drug product excipients

